## 6.8.3. Rescue Therapy

The use of rescue therapy is at the discretion of the investigator.

#### For Anemia:

Rescue therapy may be needed if Hgb fails to respond adequately despite dose adjustment or the participant is unable to tolerate daprodustat.

If a participant has a low Hgb as a result of an acute or subacute event with an identifiable cause (e.g., GI bleed, blood loss due to surgery, vascular access or trauma), the treatment should be directed to the specific cause. Daprodustat should be continued at the current dose unless Hgb is >12.0 g/dL as a consequence of a blood transfusion, in which case according to Section 4.6, the daprodustat dose should be decreased (Hgb >12.0 to  $\leq$ 12.5 g/dL) or withheld (Hgb >12.5 g/dL) and Hgb checked again at the next scheduled study visit or at an extra study visit within the next 4 weeks if a study visit is not due in that time frame.

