#### At Week 2:

Hgb will be measured to ensure there is no rapid rise following commencement of daprodustat.

- If a rapid rise is observed (>1 g in 2 weeks), the dose should be adjusted to the next lower dose step.
- If the Hgb value at Week 2 is >12.5 g/dL, daprodustat will be stopped and reintroduced at the next lower dose at a subsequent visit when the Hgb is  $\leq$ 12.0 g/dL.
- Otherwise, no change in dose is made at Study Week 2.

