#### From Week 4 until Week 52 (end of daprodustat dosing):

The dose may increase, decrease, be temporarily interrupted or stay the same based on Hgb response as shown in Table 11.

Table 11 Dose Adjustment Based on Hgb from Week 4 Onwards

Dose adjustment	Hgb status
To the next higher dose	
 
Hgb <10.0 g/dL and is not increasing (<0.5 g/dL) compared to previous visit.         OR
 
Hgb is within the target range 10.0 to 12.0 g/dL but in the opinion of the investigator the patient is still symptomatic due to their anemia.     
 
Note: if the participant is already on the highest dose step and requires a dose increase, maintain their age-defined maximum dose and re-check Hgb in 4 weeks.
 

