#### CONFIDENTIAL

214066 Protocol Amendment 02

Dose adjustment	Hgb status
To the next lower dose	
 
If the Hgb is >12.0 but ≤12.5 g/dL.         OR
 
the Hgb increased by >2.0 g/dL in 4 weeks.         OR
 
the Hgb increased by >1.0 g/dL in 2 weeks.         Note: if the participant is already on the lowest dose step and requires a dose reduction, withhold dosing and re-check Hgb in 4 weeks, dosing should restart at the lowest dose step when the Hgb is ≤12.0 g/dL.
 

To temporarily stop	If the Hgb is >12.5 g/dL, temporarily withhold dosing and check Hgb at the next study visit in 4 weeks.  Restart at the next lower dose when the Hgb is ≤12.0 g/dL.  Note: From Week 28 if the next study visit is more than 4 weeks from date of test, schedule an extra Hgb check Visit in 4 weeks.  Note: if the participant is already on the lowest dose step at the time of the temporary stop, dosing should restart at the lowest dose step at the next study visit when the Hgb is ≤12.0 g/dL.
No change	Otherwise maintain at the same dose.

The SoA (see Section 1.3) up to Week 28 requires visits every 4 weeks, where Hgb is checked. From Week 28 until Week 52 (when daprodustat treatment ceases), an extra Hgb Visit (at Week 32, 40 or 48) should be conducted 4 weeks after the previous study visit, if any of the following apply:

- At the previous study visit:
  - o A dose change was required (see Table 11).
  - O Dosing was temporarily withheld as follows:
    - Hgb >12.5 g/dL (see Table 11), or
    - the participant was already on the lowest dose in the dose adjustment algorithm and a dose reduction was required (see Table 11 and Section 4.5).
- The following occurs and the next study visit is not due within 4 weeks and a:
  - o Moderate CYP2C8 inhibitor has been prescribed (see Section 6.8).
  - o rhEPO or analogue has been administered in error (see Section 6.8.3).
  - Hgb check performed outside of the study (routine SoC or emergency) indicates that a dose change is needed (see Table 11).
- In the opinion of the investigator, the:
  - o Participant would benefit from continued 4-weekly Hgb checks.
  - Hgb is at the upper end of the target range and waiting 8 weeks for the next Hgb check is considered too long.

In addition to the above, an unscheduled (UNS) Visit at any time during the study may be conducted if, in the opinion of the investigator, the participant would benefit from

214066 Protocol Amendment 02

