### **Blood transfusions**

Blood transfusions should only be given if, in the opinion of the investigator, the benefit of transfusion outweighs the risks. Any blood transfusion (whole blood/packed red blood cells and number of units) should be recorded in the eCRF. Daprodustat can be continued at the current dose unless Hgb is >12.0 g/dL as a consequence of a blood transfusion, in which case according to Section 4.6, the daprodustat dose should be decreased (Hgb >12.0 to <12.5 g/dL) or withheld (Hgb >12.5 g/dL) and Hgb checked again at the

TMF-15144431 CONFIDENTIAL

214066 Protocol Amendment 02

next scheduled study visit or at an extra study visit within the next 4 weeks if a study visit is not due in that time frame.

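### From Week 4, Table 11 steps the dose up for Hgb below 10.0 g/dL and not increasing, while Section 6.8.3 holds it when the fall has an identified acute cause; Table 11 carries no exception

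*Protocol*

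**What the plan says.** **Section 6.8.3, For Anemia.** When low Hgb results from an acute or subacute event with a known cause (the examples are GI bleeding and blood loss from surgery, vascular access or trauma), treatment is aimed at the cause. On the study drug: "Daprodustat should be continued at the current dose unless Hgb is >12.0 g/dL as a consequence of a blood transfusion". Section 4.6 is brought in only for that high-Hgb branch.

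**Section 4.6, Table 11, from Week 4.** The dose goes to the next higher step when Hgb is below 10.0 "g/dL and is not increasing", meaning a change of less than 0.5 g/dL from the previous visit. One exception is stated: "if the participant is already on the highest dose step and requires a dose increase, maintain their age-defined maximum dose". The no-change row applies only when no other row does.

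**Section 4.6, Week 2.** A step down or a stop is possible after a rapid rise or a high value. For anything else: "Otherwise, no change in dose is made at Study Week 2".

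**Sections 6.5 and 8.1** send the reader to Sections 4.6 and 4.5 for dose changes. **Section 6.1** says the IRT is programmed with adjustments based on Hgb response. None of these mentions the cause of a low value.

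**The concern.** One participant at one visit can receive two different doses, each with support in the protocol text. A site that follows Table 11 raises the dose because of blood loss and so treats a cause unrelated to the drug as an inadequate response. Table 3 lists excessive erythropoiesis as a risk to be controlled by Hgb-guided dosing, so an unneeded increase just before Hgb recovers from a bleed is undesirable. Dose by visit is also a secondary efficacy summary (SAP Section 11.2), and that section makes no allowance for a step up made for this reason.

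**Working it through.** No planned figure needs reproducing. The check sets the two rules side by side and sizes the gap from Table 9.

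**1. Worked case, from Week 4, no transfusion.** Illustrative values: Hgb 10.8 g/dL at the previous visit and 9.2 g/dL after a surgical bleed.

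- Change = 9.2 − 10.8 = −1.6 g/dL.
- Table 11: 9.2 < 10.0 and −1.6 < 0.5, so both conditions are met and the dose steps up.
- Section 6.8.3: low Hgb from an identified acute event, so the dose is held.

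**2. How easily it is triggered.** Any fall from the target range to below 10.0 g/dL meets the step-up rule, because a fall is never an increase of 0.5. With Hgb recorded to 0.1 g/dL, the smallest triggering fall is 10.0 − 9.9 = 0.1 from a prior value of 10.0, and 12.0 − 9.9 = 2.1 from a prior value of 12.0.

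**3. Size at each step.** The inputs are the 12 to <18 years steps in Table 9. Relative change = (next step − current step) / current step.

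| Current dose (mg) | Table 11 dose (mg) | Change from hold |
|---|---|---|
| 1 | 2 | +100% |
| 2 | 4 | +100% |
| 4 | 6 | +50% |
| 6 | 8 | +33% |
| 8 | 12 | +50% |
| 12 | 16 | +33% |
| 16 | 24 | +50% |
| 24 | 24 | none (top-step note) |

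The rules differ at 7 of 8 steps.

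**4. Where there is no conflict.** At 24 mg both rules hold the dose. At Week 2 a low or falling Hgb leads to no dose change, so the conflict starts at Week 4. Above 12.0 g/dL after a transfusion, Section 6.8.3 refers to Section 4.6 and the two agree.

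**5. Search for a tie-breaker.** No sentence in Sections 4.5, 4.6, 6.1, 6.5, 7.1.3 or 8.1, or in the SAP, says which rule governs. Section 6.8.3 handles rhEPO given in error differently: there it returns the dose decision to Sections 4.5 and 4.6. For low Hgb with an acute cause it does not. This suggests the hold was a deliberate departure from the table, but it was not carried into the table. The medical monitor's IRT override at the end of Section 4.6 is described for dose changes at unscheduled visits, not for holding a dose at a scheduled one.

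**6. Possible effect on the dose summary (hypothetical).** If one participant moved from 4 to 6 mg for this reason, the sub-trial mean at that visit would shift by 2/n mg: 2.0 mg for n = 1 and 0.5 mg for n = 4. The documents do not give the split of the 4 participants by sub-trial, so n = 1 to 4 is assumed.

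**The case against.** The best reply is that Section 6.8.3 already gives direction. It is the specific rule, it names Section 4.6, and its wording confines Section 4.6 to the high-Hgb branch. Section 6.5 also ties adjustment to Hgb response, and blood loss is not a response to daprodustat. This stands as an argument for which rule should win, and it makes it wrong to say that a reader of Section 6.8.3 is left without guidance. It does not help a reader, or an IRT, working from Table 11, which applies to every low value whatever its cause.

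A second reply is that the sentence introducing Table 11 is permissive, saying only that the dose may change. That sentence lists the possible outcomes; the rows assign them, and Section 6.5 says the dose should be adjusted.

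A third reply is that little follows in practice. That stands. SAP Section 11.1.2 excludes Hgb from first rescue therapy (iron, transfusion or ESA) until 8 weeks after the last dose. Hgb after a bleed managed without those therapies stays in the analysis, but nothing is tested, and the individual plots show dose beside Hgb.

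A reader might also infer a mirror-image conflict after transfusion: Hgb still at or below 12.0 g/dL, yet stepped down because "the Hgb increased by >2.0 g/dL in 4 weeks". The documents do not support this. The hold in Section 6.8.3 is triggered by a low Hgb and has no stated duration, and the transfusion paragraph says only "Daprodustat can be continued at the current dose unless Hgb is >12.0 g/dL as a consequence of a blood transfusion", which permits continuing without requiring it. A Table 11 step-down is compatible with that.

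**Conclusion.** The inconsistency is real but minor. From Week 4, below the top dose step, Table 11 read as written raises the dose in a situation where the protocol's own specific rule holds it. The difference is one dose step, +33% to +100% in adolescents. The percentages assume the Table 9 steps, because the adolescent algorithm figure is not reproduced in the text available. The documents give no frequency of bleeding, so the number of affected visits cannot be estimated.

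A reader might infer that the reported results are compromised, but the documents do not support that. The population PK analysis plan accompanying the SAP (Section 1.1) records 4 adolescents enrolled and recruitment not to be restarted, and the analyses are descriptive. The point matters mainly for reading individual dose histories and for any reuse of the algorithm.

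**What to change.** Add one note to the step-up row of Table 11, and nowhere else: *Do not step up at a visit where the low Hgb is attributed to an identified acute or subacute event (Section 6.8.3). Keep the current dose, re-check Hgb within 4 weeks, and then apply Table 11.*

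Leave the rate-of-rise step-down, the Week 2 rapid-rise rule and the lowest-step withhold as they are. Table 3 cites a rise of more than 1 g/dL in 2 weeks as a possible contributor to serious cardiovascular risk with ESAs, so those protections should not be loosened.

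**Cost.** A true under-dose that coincides with the event is corrected about 4 weeks later. Up to Week 28 the 4-weekly visits already cover the re-check. After Week 28 it may need an extra Hgb check visit, but a step up would trigger that same visit under Section 4.6, so the note adds no visits beyond what Table 11 now implies.

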### **Blood transfusions**

Blood transfusions should only be given if, in the opinion of the investigator, the benefit of transfusion outweighs the risks. Any blood transfusion (whole blood/packed red blood cells and number of units) should be recorded in the eCRF. Daprodustat can be continued at the current dose unless Hgb is >12.0 g/dL as a consequence of a blood transfusion, in which case according to Section 4.6, the daprodustat dose should be decreased (Hgb >12.0 to <12.5 g/dL) or withheld (Hgb >12.5 g/dL) and Hgb checked again at the

TMF-15144431 CONFIDENTIAL

214066 Protocol Amendment 02

next scheduled study visit or at an extra study visit within the next 4 weeks if a study visit is not due in that time frame.

### Need for other ESA treatment

The use of rhEPOs and their analogues should be avoided during the study (Section 6.8.1). If a rhEPO is given in error, the participant can continue in the study and on study intervention (daprodustat) ensuring that Hgb is assessed within 4 weeks of the administration of the rhEPO either at the next study visit (or from Study Week 28 at an extra Hgb check Visit if the next study visit is not within that time frame). The dose of daprodustat should be adjusted if required (Section 4.5) according to the Hgb response (Section 4.6).

If in the opinion of the investigator the participant needs an alternative to study intervention (daprodustat) then the participant should permanently discontinue daprodustat but otherwise should remain in the study as planned, unless they withdraw their consent (Section 7.1). The use of rhEPO or its analogues, and if applicable the reason for study intervention cessation, should be recorded in the eCRF.

#### For Kidney Function:

Rescue intervention may be needed during the study if a participant's kidney function continues to deteriorate.

## Kidney Transplantation

Participants should be screen failed if they are scheduled for an elective living donor kidney transplant within 3 months of study entry (Section 5.2). However, participants may still enroll in the study if they are being evaluated for (or confirmed as requiring) a kidney transplant but surgery is not yet booked. In case a suitable donor is found during the course of the study, and transplantation is performed, the participant should be withdrawn from the study (Section 7.2).

## Participants in the ND Sub-trial Transitioning to Dialysis

Participants in the ND sub-trial who need to start dialysis should not be withdrawn from the study and should continue on study intervention (daprodustat), aiming to keep their Hgb within the target range of 10 to 12 g/dL (Section 4.6) as per the dose adjustment algorithm (Section 4.5).

214066 Protocol Amendment 02

# 7. DISCONTINUATION OF STUDY INTERVENTION AND PARTICIPANT DISCONTINUATION/WITHDRAWAL

CONFIDENTIAL

The definition of EOS, "study completers" and "treatment completers" is provided in Section 4.8. Discontinuation of specific sites or of the study as a whole are detailed in Section 10.1.

## 7.1. Discontinuation of Study Intervention

In rare instances, it may be necessary for a participant to permanently discontinue study intervention. Participants must be permanently discontinued from treatment with daprodustat for any of the following reasons:

- Pregnancy: Any female participant who becomes pregnant.
- Receives a diagnosis of cancer (with the exception of localized squamous cell or basal cell carcinoma).
- Need for, or use of, prohibited medications (Section 6.8.1) including use of strong inhibitors of CYP2C8 (e.g., gemfibrozil) or strong inducers of CYP2C8 (e.g., rifampin/rifampicin) for ≥14 days.
- Receives a kidney transplant (Section 6.8.3 and Section 7.2).
- Need for rhEPO or its analogues (Section 6.8.3).
- Meets the liver chemistry stopping criteria (Section 7.1.1).

Participants who discontinue study treatment prematurely for any reason should, where possible, continue in the study per protocol until the final Visit at Week 56 (except for kidney transplant participants who should be withdrawn from the study, see Section 7.2).

Reasons for premature discontinuation of study treatment must be captured in the eCRF, e.g., AE, lack of efficacy, protocol deviation, pregnancy, investigator discretion, consent withdrawal, lost to follow-up, study termination.

If a participant experiences an organ-threatening or life-threatening event, the investigator should discuss continuation of daprodustat with the GSK medical monitor.

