≥10,000 to <20,000	>150 to 300	>180 to 360	8	4	2	1
≥20,000	>300	>360	12	6	3	1.5

Abbreviations: PEG = polyethylene glycol. SC = subcutaneous, IV = intravenous, U = units, ug = micrograms

- a. Standard rhEPO IV dose (U/week) = 161/113 x (epoetin SC dose (units))/(frequency) [Besarab, 2002].
- Conversion of 250U:1μg (epoetin IV:darbepoetin alfa) utilized and rounded to the nearest available dose strength [Sterner, 2008].
- c. Conversion of 1:1.2 μg (darbepoetin alfa:methoxy PEG-epoetin beta) utilized and rounded to the nearest available dose strength [Choi, 2013].
- d. Conversion of 208 U:1 μg (epoetin IV:methoxy PEG-epoetin beta)
- e. This includes ESA users on a zero dose / dose-hold at the time of enrollment

If the actual PK data from each sub-trial age group Integrated PK Phase are in line with the PBPK model predictions, then the starting dose will be as outlined above. However, as described in Section 9.3.1, if more than 50% of the data lie outside the 95% Prediction Intervals (PIs) of the PK simulations, the PBPK model will be updated and a new scaling (pediatric to adult ratio) proposed for use in the next younger age group (i.e., Table 6, Table 7 and Table 8) will be updated for the 3 younger age groups). Note: the new

214066 Protocol Amendment 02

starting doses may be rounded to the nearest available tablet strength if new scaling is required.

See Section 4.7 for the role of the IDMC in communicating the starting dose for the 3 younger age groups.

[figure not shown]

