#### 6.8.1. Prohibited Medications

Use of any of the following prescription drugs, from Screening until 7 days after the last dose of daprodustat, is prohibited and will constitute a protocol violation:

- Strong inhibitors of CYP2C8 (e.g., gemfibrozil)
- Strong inducers of CYP2C8 (e.g., rifampin/rifampicin)
- ESA agents (rhEPO and its analogues‡ and other HIF-PHIs if approved for pediatric use during the conduct of this study).
- No other investigational agents (including other HIF-PHIs) or devices are permitted from study entry through completion of the study.

For participants receiving ESA treatment prior to study entry, the investigator should schedule the Day 1 Visit (and Screening Visit, if intending Screening and Day Visits are the same day) to coincide, as closely as possible, with the date of the next scheduled ESA administration. Examples are provided in the table below:

ESA Schedule	Last ESA Dose	Day 1 (Baseline)
TIW	Monday	Wednesday
	Tuesday	Thursday
	Wednesday	Friday
Weekly	Wednesday	Following Wednesday
Every two weeks	2 weeks before Day 1	2 weeks after last ESA dose
Every four weeks	4 weeks before Day 1	4 weeks after last ESA dose

214066 Protocol Amendment 02

In general, GSK study participants can be vaccinated against COVID-19 using vaccines authorized via limited regulatory mechanisms (e.g., Emergency Use Authorization) or approved via accelerated or full approval mechanisms. Use of other candidate COVID-19 vaccines that have not received limited, accelerated, or full authorization/approval, and are only in use as part of a clinical trial, are not allowed.

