# 7.2. Key Secondary Estimand

The secondary efficacy target estimand is the Hgb endpoints at each study time point in children and adolescents with anemia of CKD in each sub-trial (D/ND), regardless of disruptions or delays in study intervention whilst still continuing study intervention (daprodustat) and before any unplanned ESA therapy or rescue therapy.

- Population: Children and adolescent participants with anemia associated with CKD
- Variable: At each study timepoint:
  - Hqb value
  - Change in Hgb value from baseline
  - Hgb above, within and below the target range (10 to 12 g/dL)
- Population-level summary: At each study timepoint:
  - Summary statistics of Hgb value, including number of observed Hgb values, number of missing Hgb values, mean, SD, and median of the observed Hgb values.
  - Mean change in Hgb value from baseline, including number of observed Hgb values, number of missing Hgb values, mean, SD, and median.
  - Number and percentage of participants with Hgb above, below and within the target range (10 to 12 g/dL).
- Intercurrent events:

This document is confidential.

SAP Version: SAP V1.0 23-Jan-2025

Controlled Document ID: CC Effective Date 31-Aug-2020

Sponsor: GlaxoSmithKline Research & Development Limited; Protocol No.: 214066/Protocol Amendment 02

- Disruptions and delays in study intervention will be addressed using treatment policy strategy, where the treatment effect of interest is determined regardless of the occurrence of the ICE and no imputations will be conducted.
- Permanent study intervention discontinuation due to any reason will be addressed using while-on-treatment strategy, where unobserved Hgb results beyond study intervention discontinuation will not be imputed or included for analysis.
- Unplanned use of ESA therapy within the trial will be addressed using while-on-treatment strategy, where the Hgb values will be excluded for the period of 8 weeks following the occurrence of the intercurrent event from analysis and will not be imputed.
- Intermittent use of rescue therapy within the trial will be addressed with while-ontreatment policy strategy, where the Hgb values from the date of initial use of rescue therapy until 8 weeks after the last dose of rescue therapy will be excluded from analysis and will not be imputed.
- Kidney transplantation or death will be handled using while-on-treatment strategy, where
  data up the time of transplantation or death will be used for analysis, no missing Hgb

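### Section 7.1 as worded makes any use of rhEPO a mandatory permanent stop of daprodustat, while Section 6.8.3 and the Hgb analysis rules let a participant given rhEPO in error continue

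*Protocol*

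**What the plan says.** **Protocol 7.1.** The list opens "Participants must be permanently discontinued from treatment with daprodustat for any of the following reasons". One reason begins "Need for, or use of, prohibited medications (Section 6.8.1", goes on to strong inhibitors and strong inducers of CYP2C8, and ends with a duration of at least 14 days. A separate bullet names only the *need* for rhEPO or its analogues and refers to 6.8.3.

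**Protocol 6.8.1.** rhEPO and its analogues are on the prohibited list together with the CYP2C8 drugs. Use "from Screening until 7 days after the last dose of daprodustat, is prohibited and will constitute a protocol violation". For participants already on an ESA, the same section asks that Day 1 be set "to coincide, as closely as possible, with the date of the next scheduled ESA administration", with examples for three-times-weekly (TIW), weekly, 2-weekly and 4-weekly schedules.

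**Protocol 6.8.3, need for other ESA treatment.** "If a rhEPO is given in error, the participant can continue in the study and on study intervention (daprodustat", provided that Hgb is checked within 4 weeks. The next paragraph covers a different case: a participant who needs an alternative to daprodustat stops it permanently but stays in the study.

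**Protocol 4.6 and Schedule of Activities note b.** rhEPO given in error is one of the triggers for an extra Hgb visit in the second half of treatment.

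**Protocol 3.2, SAP 7.2 and SAP 11.1.2.** After unplanned ESA use the strategy is while-on-treatment, "where the Hgb values will be excluded for the period of 8 weeks following the occurrence of the intercurrent event from analysis". After permanent discontinuation, SAP 11.1.2 excludes every later Hgb value, even if it was collected.

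**The concern.** A stopping rule should give one answer for one event. Here a single rhEPO dose given by mistake can be read two ways. Under 7.1 it is use of a prohibited medication and ends daprodustat for good. Under 6.8.3 it is an error after which daprodustat goes on with an Hgb check.

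The choice decides three things: the participant's treatment, the count of treatment discontinuations, and which Hgb values enter the secondary efficacy summaries. The two SAP exclusion rules differ greatly in length, so the classification of one event can remove a short stretch of data or everything that follows.

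**Working it through.** The plan gives no figure to reproduce on this point. The check is a comparison of texts and two small counts.

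**1. What the 7.1 bullet covers.** The bullet applies to need for, or use of, anything in 6.8.1, and ESAs are in 6.8.1. The 14-day duration follows the words on CYP2C8 inhibitors and inducers and most naturally limits only those drugs. The bullet has no exception for administration in error. The reasons in 7.1 are alternatives, any one of which is enough, so the narrower rhEPO bullet does not narrow the broader one.

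**2. The texts side by side, for one rhEPO dose given in error.**

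| Place | Consequence |
|---|---|
| Protocol 7.1, prohibited-medication bullet | Permanent stop |
| Protocol 7.1, rhEPO bullet | Silent (covers need only; refers to 6.8.3) |
| Protocol 6.8.3 | Daprodustat can continue; Hgb within 4 weeks |
| Protocol 4.6 and Schedule of Activities note b | Extra Hgb visit, which supports a dosing decision |
| Protocol 3.2, SAP 7.2, SAP 11.1.2 | Hgb excluded for 8 weeks, then counted again |

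Only the first row requires a stop. The last three assume that dosing goes on.

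**3. Hgb values at stake, for an error at Week 12 (a week chosen for illustration).** Section 4.6 schedules Hgb at Weeks 2, 4, 8, 12, 16, 20, 24, 28, 36, 44 and 52.

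- Scheduled on-treatment values after Week 12: Weeks 16, 20, 24, 28, 36, 44 and 52, so 7.
- 8-week rule: the window ends at 12 + 8 = Week 20. Weeks 16 and 20 are dropped, and 7 − 2 = 5 are kept.
- 7.1 read literally, with the SAP 11.1.2 discontinuation rule: all 7 are dropped, 0 are kept, and one treatment discontinuation is added.

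These are nominal weeks. Week 20 sits on the edge of the window, so an actual visit one or two days late could fall just outside it. Extra and unscheduled visits are not counted.

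**4. The start of the ESA ban in 6.8.1 (minor).** Let *g* be the days from Screening to Day 1 (0 to 28 permitted, so 29 values) and *k* the days from the last ESA dose to Day 1 in the 6.8.1 examples. That dose falls after Screening, inside the banned period, when *g* > *k*.

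| ESA schedule | *k* (days) | Gaps with a collision | Count of 29 |
|---|---|---|---|
| TIW | 2 | 3 to 28 | 26 |
| Weekly | 7 | 8 to 28 | 21 |
| 2-weekly | 14 | 15 to 28 | 14 |
| 4-weekly | 28 | none | 0 |

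With same-day Screening and Day 1 (*g* = 0) no schedule collides. The counts say which gaps are affected, not how often sites would use them.

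**The case against.** The best answer is that 7.1 has its own rhEPO bullet. It is limited to need and points to 6.8.3, where error and need are treated separately. If the prohibited-medication bullet already caught every ESA use, the rhEPO bullet would be redundant. Section 4.6, note b and the estimand text all follow 6.8.3, and the 14-day condition could be stretched over the whole bullet so that one erroneous dose would not meet it. This is good evidence of intent, and it stands as that. It does not remove the conflict: the reasons are alternatives, the broader bullet adds *use* to *need*, and no sentence takes an error out of it.

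It can also be said that little now depends on it. The population PK analysis plan (Section 1.1) reports that recruitment ended with 4 adolescents, who continued to the protocol-defined end. The documents report no rhEPO error and no diverging site practice. That limits the realized effect, not the inconsistency.

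Three stronger readings are tempting and are not supported:

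- *That 6.8.1 flatly contradicts its own Day 1 examples.* The ESA item carries a footnote marker, and the amendment history (Appendix 7) says that the footer was added to explain Day 1 scheduling. The examples are very probably a qualification of the ban, and they collide with it only when a separate Screening visit precedes the last ESA dose.
- *That a literal ban would move participants to the lowest starting-dose row.* Footnote e to Table 8 reads "This includes ESA users on a zero dose / dose-hold at the time of enrollment", and Table 7 has the same note. Nothing says that an ESA stop caused by screening counts as such a hold, so no shift in starting dose can be derived.
- *That the primary endpoint is at risk.* The primary estimand follows safety events regardless of discontinuation, and a stop for a prohibited medication is not in itself an AE leading to discontinuation.

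**Conclusion.** The inconsistency between 7.1 and 6.8.3 is real on the wording, and it should be corrected. In the Week 12 example it decides whether two or all seven of the remaining scheduled Hgb values are excluded, and whether a treatment discontinuation is recorded. The difference would be larger for an earlier error and smaller for a later one.

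This rests on two readings: that the 14-day condition belongs to the CYP2C8 drugs, and that the 7.1 reasons apply independently. Both are the natural reading, but neither is the only possible one. The likely intent is that 6.8.3 governs. The effect is confined to treatment continuation, the discontinuation count and the secondary Hgb summaries. With 4 participants enrolled and no such event reported, the realized effect may be nil.

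The ESA-ban point is minor and conditional. It arises for TIW, weekly and 2-weekly schedules when Screening is a separate visit before the last scheduled ESA dose. There the text does not expressly exempt doses that its own scheduling advice presupposes.

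**What to change.** Reconcile the prohibited-medication bullet in 7.1 with 6.8.3, 4.6, and SAP 7.2 and 11.1.2. State in 7.1 whether rhEPO given in error falls inside or outside the mandatory stop, and make clear which drugs the 14-day condition covers. If it falls inside, 6.8.3, 4.6 and note b need to change, and the SAP should say that the discontinuation rule overrides the 8-week rule. If it falls outside, the SAP can stand. Which clinical rule is right is for the sponsor to decide.

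In 6.8.1, reconcile the start of the ESA ban with the Day 1 scheduling text by saying in words how ESA doses between Screening and Day 1 are treated.

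The cost is a few sentences, with no new data, visits or analyses. As recruitment has ended, the practical minimum is to state in the report which rule was applied to any unplanned ESA use among the enrolled participants.
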